Leukopenia	
Although there is a perceived theoretical risk that GM-CSF blockade may affect maturation of leukocytes and their precursors, mice lacking GM-CSF do not develop neutropenia or show any major perturbation of hematopoiesis [Stanley, 1994].
 
Non-clinical & Clinical Data:
 
There have been no reports of neutropenia or decreases in leukocytes in the non-clinical and clinical GSK3196165 program.
	
Subject selection (see Section 5.2):
 
 • Subjects with significant leukopenia ($\leq 3.0 \times 10^9/L$); thrombocytopenia (platelet count $\leq 100 \times 10^9/L$); neutropenia (absolute neutrophil count $\leq 1.5 \times 10^9/L$); lymphocytopenia ($\leq 0.5 \times 10^9/L$) within 4 weeks prior to Day 1 are not permitted to enter the study. 
Subject monitoring:
 
 • A full blood count (with differential) will be performed at regular intervals throughout the study (ref. Time and Events Table, Section 7.1). • Grade 3 or greater neutropenia is categorised as an AESI. 
Withdrawal criteria:
 
 • In the events of significant leukopenia ($< 2.0 \times 10^9/L$); neutropenia (absolute neutrophil count $< 1.0 \times 10^9/L$); lymphocytopenia ($< 0.5 \times 10^9/L$), study medication should be

Potential Risk of Clinical Significance	Summary of Data/Rationale for Risk	Mitigation Strategy
		discontinued and the subject withdrawn from the study.

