5.4. Withdrawal/Stopping Criteria

The following actions must be taken in relation to a subject who fails to attend the clinic for a required study visit:

- The site must attempt to contact the subject and re-schedule the missed visit as soon as possible.
- The site must counsel the subject on the importance of maintaining the assigned visit schedule and ascertain whether or not the subject wishes to and/or should continue in the study.
- In cases where the subject is deemed ‘lost to follow up’, the investigator or designee must make every effort to regain contact with the subject (where possible, 3 telephone calls and if necessary a certified letter to the subject’s last known mailing address). These contact attempts should be documented in the subject’s medical record.
- Should the subject continue to be unreachable, only then will he/she be considered to have withdrawn from the study with a primary reason of “Lost to Follow-up”.

A subject may withdraw from study treatment at any time at his/her own request, or may be withdrawn at any time at the discretion of the investigator for safety, behavioral or administrative reasons.

In addition, study medications will be discontinued and the subject withdrawn from the study in the event of any of the following:

- All serious or opportunistic infections.
- Pregnancy.
- Confirmed PAP.
- Severe or serious hypersensitivity reactions, including anaphylaxis.
- If the liver chemistry stopping criteria (Section 5.4.1) or QTc stopping criteria (Section 5.4.2) are met.
- Persistent or recurrent hematological laboratory abnormalities (see Section 5.5.2).
- Detected (≥ 2.1 log copies/mL) HBV DNA for subjects who have positive anti-HBs antibody.
- Other serious or severe adverse events, at the discretion of the investigator, after consultation with the Medical Monitor.

[figure not shown]
If a subject withdraws from the study, he/she may request destruction of any samples taken, and the investigator must document this in the site study records.

Any subject who withdraws must complete an early withdrawal visit, and the 10-week follow-up visit (from withdrawal visit).

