5.5.2. Hematologic abnormalities

The following hematological laboratory abnormalities require temporary suspension of study medications and prompt retesting, ideally within 3-5 days:

- White blood cell count < 2.0 x 10⁹/L

- Absolute neutrophil count $< 1.0 \times 10^9/L$
- Lymphocyte count $< 0.5 \times 10^9/L$

Study medication should not be restarted until the parameters are above these values, and subjects should be followed as appropriate until resolution of the event.

If these abnormalities are persistent (present on ≥ 2 sequential tests), or occur recurrently (on 2 separate occasions), study medications will be permanently discontinued and the subject withdrawn from the study.

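### At identical blood-count limits, the leukopenia row of the Protocol 4.6.1 risk table withdraws the subject, while Section 5.5.2 suspends, retests and withdraws only if the abnormality is persistent or recurrent

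*Protocol*

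**What the plan says.** Four places in the current protocol bear on a low blood count during treatment.

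- **Section 4.6.1, Risk Assessment, leukopenia row, withdrawal criteria.** The rule opens "In the events of significant leukopenia" and gives limits for leukocytes, neutrophils and lymphocytes. Its consequence is that study medication should be "discontinued and the subject withdrawn from the study". It mentions no retest, persistence or recurrence, and does not refer to Section 5.5.2.
- **Section 5.5.2, Hematologic abnormalities.** Low counts "require temporary suspension of study medications and prompt retesting, ideally within 3-5 days". Medication may resume once the counts are back above the limits. Permanent discontinuation and withdrawal follow if the abnormality is found on at least two sequential tests or on two separate occasions.
- **Section 5.4, Withdrawal/Stopping Criteria.** The hematology entry in the list of reasons for withdrawal reads "Persistent or recurrent hematological laboratory abnormalities (see Section 5.5.2".
- **Section 6.1, Table 2, dosing instructions.** For discontinuing or interrupting the investigational product, sites are referred to Sections 5.4 and 5.5. Section 4.6.1 is not mentioned.

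**The concern.** This is a stopping rule for a risk that the protocol names, so a site needs one answer when the first low count arrives. As written, the risk table ends that subject's participation, while Section 5.5.2 leaves open a return to dosing. Section 7 allows no waivers except for immediate safety concerns, so a site that follows either section departs from the other.

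Two subjects with the same laboratory history could then be handled differently because their sites relied on different sections. In the analysis this would affect:

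- subject disposition and reasons for stopping treatment (SAP Tables 1.1 and 1.2);
- adverse events leading to withdrawal or permanent discontinuation (SAP Tables 3.8 and 3.9), where the low count is recorded as an adverse event;
- the primary PK parameters, which SAP Table 4 defines from the Visit 10 (Day 71) dose onward;
- the binary efficacy endpoints, where SAP 11.6.2 counts early withdrawal as failure.

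**Working it through.** No figure in the plan needs reproducing. The check sets the rules side by side and then sizes the effect of one subject.

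**Step 1. Limits (x 10^9/L)**

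| Count | 4.6.1, leukopenia row | 5.5.2 |
|---|---|---|
| Leukocytes | < 2.0 | < 2.0 |
| Neutrophils | < 1.0 | < 1.0 |
| Lymphocytes | < 0.5 | < 0.5 |

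All three agree in value and direction, so the two rules cannot be read as covering different degrees of severity.

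**Step 2. Action and end result**

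| Course of the low count | 4.6.1 | 5.5.2 (and 5.4) |
|---|---|---|
| First low value, on the day | Stop and withdraw | Hold and retest |
| Single low value that recovers | Withdrawn | May restart and stay in the study |
| Low on at least 2 sequential tests | Withdrawn | Withdrawn, after the retest |
| Recovers, then low on a second occasion | Withdrawn at the first | Withdrawn at the second |

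Both rules stop dosing at the first low value. Both end in withdrawal if it persists or recurs, though 5.5.2 gets there later. The final outcome differs only in the second row: an isolated value that recovers.

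**Step 3. Can the risk-table row be read as shorthand for 5.5.2?** The word *significant* adds no condition, because the bracketed numbers define it and they are the 5.5.2 limits. The other withdrawal entries in the table (serious or opportunistic infection, confirmed pulmonary alveolar proteinosis (PAP), severe or serious hypersensitivity, pregnancy) all match Section 5.4. The PAP row also spells out a step of suspension and referral before withdrawal. The leukopenia row has no such step, and it is the only withdrawal entry in the table that departs from 5.4.

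**Step 4. Effect of one subject.** Planned group size is 10 (Protocol 4.1).

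- Discontinuation: 1/10 = 10%, so one subject moves an arm's observed proportion by 10 percentage points, for example from 0/10 to 1/10. Protocol Table 4 gives the exact 95% interval for 1 of 10 as 0.3% to 44.5%.
- PK: a subject on active drug withdrawn before Day 71 receives no Visit 10 dose and so has no profile from which SAP Table 4 parameters can be derived. A subject held and restarted can have one. That is 1 of 10 in a dose group and, with 3 x 10 = 30 active subjects, 1/30 = 3.3% of those planned for the power model. SAP 11.6.1 says withdrawn subjects were not replaced.

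**Step 5. Opportunity.** In the SAP Appendix 1 schedule, post-baseline hematology falls at Weeks 2, 4, 8, 12 and 22. The last dose is at Week 10, so three scheduled tests (Weeks 2, 4 and 8) can affect a later dose. From Week 12 the difference is only whether the subject stays in follow-up. Exclusion criterion 24 bars lymphocytes of 0.5 or lower, so the lymphocyte entry limit and stopping limit coincide. For leukocytes the gap is 3.0 - 2.0 = 1.0 and for neutrophils 1.5 - 1.0 = 0.5. A trigger is therefore possible, but Section 4.6.1 reports no neutropenia or leukocyte decrease in the programme to date. No expected rate can be taken from the documents.

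**The case against.** The strongest reply is that the operative rule can be found. Section 6.1, Table 2 sends sites to 5.4 and 5.5 to discontinue or interrupt dosing. Section 5.4 lists only persistent or recurrent abnormalities and points to 5.5.2. These three places form one consistent chain. Section 4.6.1 belongs to the benefit-risk discussion and is not a full list of stopping rules: it has no row for the liver, QTc or HBV-DNA criteria in 5.4. Its verb is also softer, *should be* against *require* and *will be*.

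Much of this stands. The risk-table row is the outlier, and a reader who infers that sites hold opposite instructions of equal standing goes further than the documents allow. Dosing stops at the first low value under both texts, and a persistent or recurrent abnormality ends in withdrawal under both.

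The objection does not remove the conflict. The row is labelled as withdrawal criteria and gives specific limits. Its *should be* is also the verb used in the same table for confirmed PAP and pregnancy, which nobody would take as optional. The reference in Table 2 shows where to look, but neither it nor any other text says that 5.4 and 5.5 override 4.6.1.

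**Conclusion.** The inconsistency is real, lies in current protocol text, and concerns a safety stopping rule. It is confined to a first or isolated low count that recovers: a site following 4.6.1 would withdraw a subject whom 5.5.2 would allow to restart. Each such subject is 1 of 10 in an arm for discontinuation counts. If on active drug and withdrawn before Day 71, the subject is also 1 of 10 for PK after the last dose. These sizes assume the planned 10 per group and at least one site acting on the risk table.

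Two stronger readings are not supported. One is that every value below a limit leads to a different result; values that persist or recur end in withdrawal either way. The other is that one subject amounts to 10% of a discontinuation rate; the subject is 10 percentage points of a 10-subject arm. With no frequency stated and none reported to date, the effect on the trial's results may be nil. The case for correction rests on having one clear safety rule. Calling the risk-table row the outlier describes the text and does not judge which rule is clinically right.

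**What to change.** Reconcile the leukopenia row of Section 4.6.1 with Section 5.4, Section 5.5.2 and the dosing instructions in Section 6.1, Table 2, so that one rule for a first low count appears in all four. If the risk table is meant only as a summary, a cross-reference from that row to the governing section would keep the texts aligned. Which rule applies to a first low count is a clinical decision for the sponsor and is not proposed here. The cost is protocol wording only: no change to sample size, assessments or analysis.

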4.6.2. Benefit Assessment

GM-CSF plays a key role in initiation and progression of inflammation in RA and indirectly increases the destruction of the bone and cartilage. GSK3196165 binds human GM-CSF, inhibits GM-CSF mediated responses in vitro and reduces inflammatory responses in rat arthritis models. GSK3196165 has shown evidence of efficacy in a Phase 1b/2a trial (Study MSC-1001) in subjects with active RA [Behrens, 2015]. In addition, mavrilimumab (an anti-GM-CSF α -subunit receptor mAb), has also shown substantial activity in RA subjects who had an inadequate response to MTX in studies of up to 24 weeks of dosing [Burmester, 2013; Burmester, 2014]. These data support the clinical evaluation of GSK3196165 in subjects with RA.

4.6.3. Overall Benefit:Risk Conclusion

Current preclinical and clinical data with GSK3196165 indicates that it binds and inhibits the function of GM-CSF and that this inhibition may have clinical utility in the treatment of inflammatory and autoimmune diseases, such as RA.

Key potential risks are those described above that may be associated with inhibition of GM-CSF (e.g., pulmonary toxicity, infection) and those associated with administration of a therapeutic monoclonal antibody (e.g. allergic reactions). Appropriate safety monitoring will be undertaken in studies of GSK3196165 to proactively address and mitigate the potential risks. Recent data with mavrilimumab administered for 24 weeks in combination with MTX in subjects with active RA [Burmester, 2014] provides further support that targeting this pathway is associated with an acceptable benefit:risk profile.

Given the safety monitoring that has been put in place to minimize risk to subjects participating in clinical studies of GSK3196165, the potential risks identified are justified by the potential benefits that may be afforded to patients with RA.

5. SELECTION OF STUDY POPULATION AND WITHDRAWAL CRITERIA

Specific information regarding warnings, precautions, contraindications, adverse events, and other pertinent information on the GSK investigational product or other study treatment that may impact subject eligibility is provided in the IB.

Deviations from inclusion and exclusion criteria are not allowed because they can potentially jeopardize the scientific integrity of the study, regulatory acceptability or subject safety. Therefore, adherence to the criteria as specified in the protocol is essential.

5.1. Inclusion Criteria

A subject will be eligible for inclusion in this study only if all of the following criteria apply:

AGE
1. Age ≥ 20 years at the time of signing informed consent.
TYPE OF SUBJECT AND DIAGNOSIS INCLUDING DISEASE SEVERITY
2. Japanese RA subjects who meets ACR/EULAR 2010 RA Classification Criteria.
3. Functional class I, II or III defined by the 1992 ACR Classification of Functional Status in RA.
4. Disease duration of ≥ 12 weeks (time from onset of patient-reported symptoms of either pain or stiffness or swelling in hands, feet or wrists).
5. Swollen joint count of ≥ 4 (66-joint count) and tender joint count of ≥ 4 (68-joint count) at screening and at Day 1.
6. DAS28(CRP) ≥ 3.2 at screening.
7. C-Reactive Protein (CRP) ≥ 0.3 mg/dL at screening.
8. Must have previously received MTX (8-16 mg weekly) orally for at least 12 weeks before screening, with a stable and tolerated dose for ≥ 4 weeks prior to Day 1.
WEIGHT
9. Weight ≥ 40 kg.
SEX
10. Male or female subjects are eligible to participate so long as they meet and agree to abide by the contraceptive criteria detailed in Appendix 2 .
INFORMED CONSENT
11. Written informed consent prior to any of the screening procedures including discontinuation of prohibited medications.

OTHER SAFETY-RELATED
12. Willing to continue or initiate treatment with oral folic acid (5 mg/week) and be treated during the entire study (mandatory co-medication for MTX treatment).
13. $D_{LCO} \geq 60\%^{1)}_{predicted}$; forced expiratory volume in 1 second (FEV_1) $\geq 70\%_{predicted}$; forced vital capacity (FVC) $\geq 80\%_{predicted}$.
1) For subjects with D_{LCO} values $\geq 60\%$ to $< 70\%$, a baseline chest high-resolution computed tomography (HRCT) must be performed during the screening period, and it is recommended that the subject be reviewed by a local pulmonologist to exclude significant pre-existing respiratory disease.
14. No evidence of active or latent infection with Mycobacterium tuberculosis (TB), as defined by all of the following:
1) No history of active or latent TB infection irrespective of treatment status.
2) A negative T-spot test within 4 weeks of baseline (Day 1).
3) Chest X-ray within 12 weeks of Day 1, locally read by a radiologist, with no evidence of current or previous pulmonary tuberculosis. NB: If there is suspicious of risk for TB infection because of recent close contact with persons who have active TB prior to study enrolment the subject will be referred to a TB physician to undergo additional evaluation.

5.2. Exclusion Criteria

A subject will not be eligible for inclusion in this study if any of the following criteria apply:

CONCURRENT CONDITIONS/MEDICAL HISTORY (INCLUDES LIVER FUNCTION AND QTc INTERVAL)

 1. Pregnant or lactating women. 2. History of other inflammatory rheumatological or autoimmune disorders, other than Sjögren's syndrome secondary to RA. 3. History of any respiratory disease which (in the opinion of the investigator) would compromise subject safety or the ability of the subject to complete the study (e.g. significant interstitial lung disease, such as pulmonary fibrosis, chronic obstructive pulmonary disease (COPD), moderate-severe asthma, bronchiectasis, previous PAP). 4. Clinically-significant or unstable (in the opinion of the investigator) persistent cough or dyspnea that is unexplained. 5. QT interval corrected for heart rate (QTc) > 450msec or QTc > 480msec for subjects with bundle branch block.

The QTc is the QT interval corrected for heart rate according to Fridericia's formula (QTcF).

6. Liver function tests: alanine aminotransferase (ALT) $\geq 1.5 \times$ upper limit of normal (ULN); aspartate transaminase (AST) $\geq 1.5 \times$ ULN; alkaline phosphatase and bilirubin $\geq 1.5 \times$ ULN (isolated bilirubin $> 1.5 \times$ ULN is acceptable if bilirubin is fractionated and direct bilirubin $< 35\%$).
7. Current active liver or biliary disease (with the exception of Gilbert's syndrome or asymptomatic gallstones or otherwise stable chronic liver disease per investigator assessment).
8. Clinically significant unstable or uncontrolled acute or chronic disease (e.g., cardiovascular including uncompensated congestive cardiac failure New York Heart Association [NYHA] III or IV, myocardial infarction within 12 months, unstable angina pectoris, uncontrolled hypertension, uncontrolled hypercholesterolemia) pulmonary, hematologic, gastrointestinal (including Crohn's Disease or ulcerative colitis), hepatic, renal, neurological, psychiatric, malignancy, endocrinological or infectious diseases, which, in the opinion of the investigator, could confound the results of the study or put the subject at undue risk.
9. A history of malignant neoplasm within the last 10 years or breast cancer within the last 20 years, except for non-melanoma skin cancers that have been excised and cured or carcinoma in situ of the uterine cervix.
10. Kidney disease: Current or history of renal disease, or estimated creatinine clearance $< 60 \text{ mL/min}/1.73 \text{ m}^2$ (MDRD formula) or serum creatinine $> 1.5 \times$ ULN within 4 weeks of Day 1.
11. Hereditary or acquired immunodeficiency disorder, including immunoglobulin deficiency.
12. History of infected joint prosthesis at any time, with the prosthesis still in situ. History of leg ulcers, catheters, chronic sinusitis or recurrent chest or urinary tract infections.
13. Active infections, or history of recurrent infections (excluding recurrent fungal infections of the nail bed), or have required management of acute or chronic infections, as follows:
 - i) Currently on any suppressive therapy for a chronic infection (such as tuberculosis, pneumocystis, cytomegalovirus, herpes simplex virus, herpes zoster and atypical mycobacteria).

OR

 - ii) Hospitalization for treatment of infection within 26 weeks of Day 1.

OR

 - iii) Use of parenteral (IV or IM) antimicrobials (antibacterials, antivirals, antifungals, or antiparasitic agents) within 26 weeks of Day 1 or oral

antimicrobials within 2 weeks of Day 1.

14. A vaccination (live or attenuated) within 30 days of Day 1 or Bacillus Calmette-Guérin (BCG) vaccination within 1 year of Day 1, or a live vaccination planned during the course of the study (including follow-up period).
15. Any surgical procedure, including bone or joint surgery/synovectomy within 12 weeks prior to Day 1 or any planned surgery within the duration of the study (including follow-up period).

CONCOMITANT MEDICATIONS

16. Use of prohibited medications Prior to AND throughout the study:
 - Any conventional DMARDs other than MTX (including sulfasalazine, bucillamine, ivermectin, tacrolimus) should be withdrawn at least 2 weeks prior to Day 1.
 - Subjects may require longer to discontinue azathioprine or leflunomide prior to Day 1:
 - i) Azathioprine must be discontinued \geq 4 weeks prior to randomization.
 - ii) Leflunomide must be discontinued \geq 12 weeks prior to Day 1 (or \geq 14 days after 11 days of standard cholestyramine or activated charcoal washout).
 - For these subjects, written informed consent for the study must be obtained prior to beginning the screening period. However, other screening assessments, other than consent, must occur within 4 weeks prior to Day 1.
 - Any biologic agents (such as TNF inhibitors [including adalimumab, etanercept, infliximab, certolizumab pegol, golimumab] or non-TNF inhibitors [including abatacept, rituximab, tocilizumab, belimumab]).
 - Any Janus kinase (JAK) inhibitors (such as tofacitinib).
 - Any anti-rheumatic investigational compounds.
 - Any alkylating agents (such as cyclophosphamide).
 - Plasmapheresis or intravenous immunoglobulin (IVIG) within 26 weeks of Day 1.

17. Corticosteroids:
 - Any IM, IV or IA corticosteroids within 8 weeks of Day 1.
 - Oral corticosteroids:
 - Any treatment with >10 mg/day dose oral prednisolone (or equivalent) within 4 weeks of Day 1.
 - New oral corticosteroid or changes in corticosteroid dose within the 4 weeks prior to Day 1. (New topical steroids and immunosuppressive agents (e.g., eye drops, creams) are permitted).

18. Non-steroidal anti-inflammatory drugs (NSAIDs):

- New or change in dose of NSAID within 2 weeks of Day 1.

19. Any non-anti-rheumatic investigational treatment must be discontinued for at least 4 weeks or 5 half-lives, whichever is longer, prior to Day 1.

RELEVANT HABITS

20. Have current drug or alcohol abuse or dependence, or a history of drug or alcohol abuse or dependence within a year prior to Day 1.

CONTRAINdicATIONS

21. History of sensitivity to any of the study treatments, or components thereof or a history of drug or other allergy that, in the opinion of the investigator or Medical Monitor, contraindicates their participation.

DIAGNOSTIC ASSESSMENTS AND OTHER CRITERIA

22. Abnormal chest X-ray within 12 weeks of Day 1 (locally read and reported by a radiologist) judged by the investigator as clinically-significant.

23. Any Grade 3 or 4 hematology or clinical chemistry laboratory abnormality [[CTCAE](#), 2009 v4.0] within 4 weeks of Day 1.

24. Hemoglobin ≤ 9 g/dL; white blood cell count $\leq 3.0 \times 10^9/L$; platelet count $\leq 100 \times 10^9/L$; absolute neutrophil count $\leq 1.5 \times 10^9/L$; lymphocyte count $\leq 0.5 \times 10^9/L$ within 4 weeks of Day 1.

25. Serologic evidence of current/previous Hepatitis B virus (HBV) infection based on the results of testing for Hepatitis B surface antigen (HBsAg) and anti-Hepatitis B core (anti-HBc) antibody as follows within 4 weeks of Day 1.

- Subjects positive for HBsAg and/or positive for anti-HBc antibody (regardless of anti-HBs antibody status) are excluded.
- Subjects with positive anti-HBs antibody and HBV-DNA (≥ 2.1 log copies/mL) are excluded.

26. Hepatitis C: Positive test for Hepatitis C virus (HCV) antibody confirmed on a subsequent blood sample by RNA-PCR assay within 4 weeks of Day 1.

- Subjects who are positive for Hepatitis C antibody and negative when the Hepatitis C RNA-PCR assay is performed on a subsequent sample will be eligible to participate. Subjects who are positive for Hepatitis C antibody and have a positive result for the HCV when the Hepatitis C RNA-PCR assay is performed on the subsequent sample will not be eligible to participate.

27. Positive serology for human immunodeficiency virus (HIV) 1 or 2 (within 4 weeks of Day 1).

